5. MONITORING AND AUDIT

Study Monitoring

The study will be monitored by the Principal Investigator at periodic intervals during the course of the study to ensure that the study is being conducted according to Good Clinical Practice.

The Investigators will be contacted by the PI on a regular basis. On this occasion, the progress of the study will be discussed with the Investigator and the CRFs will be checked for completeness and consistency and to verify compliance with the study protocol.

6. SUBJECT TERMINATION/WITHDRAWAL PROCEDURES

All efforts will be made to determine the reason(s) why a patient is withdrawn from the study. Subjects could be withdrawn from the study if any of the following occur:

1. Subject fails to substantially comply with the protocol requirements;
2. Subject develops a serious adverse reaction. The Study Investigator will immediately notify the PI and information will be recorded on a Serious Adverse Event Form (Appendix 3);
3. Subject elects to terminate participation in the study. Participation in the study is voluntary. A subject has the right to withdraw from the study at any time for any reason.

The Investigator may terminate the study at any time if the risk-benefit ratio is no longer favourable. Before discontinuation, the Investigator should inform the PI and ask for advice. If the Investigator is concerned about continuation of the study, his/her concerns should be transmitted immediately to the PI.

7. DOCUMENTATION AND DATA MANAGEMENT

Data collection in the case report form (CRF)

All study data will be recorded in the case report forms identified by the subject number. Only the principal investigator, co-investigators, or designated study personnel may make entries in the case report forms.

The Investigator has to identify all data that were directly recorded into the CRF and to be considered to be source data.

The CRFs will be checked for completeness and plausibility by the PI. The Investigator will resolve any queries.

Investigator Site File (ISF)

The ISF includes all documents that are required for the clinical study. During monitoring, the ISF will be checked regularly for completeness and actuality. After the clinical trial is finished or stopped, the ISF has to be stored 15 years in the study center.

Data Management

Data extraction from CRFs into a single, electronic database is performed by examiners. Discrepancies are to be clarified and corrected by authorized persons by means of documented data queries between Statistician and Investigator(s).

After the study is finished and before data are analyzed, a blind data review meeting will be held between the investigator and the statistician. When the database has been declared to be complete and accurate, it will be locked. Any changes to the database after this procedure can only be made by joint written agreement among the clinical trial leader, the trial statistician, and the co-investigators.

8. ADVERSE EXPERIENCES/EVENTS

Subjects will be informed of any possible adverse reactions which they could experience and will be instructed to immediately report any event to the investigator. The investigators will record any and all adverse reactions and report this documentation to the Principal Investigator. In the event of an adverse experience, emergency or other problems or questions regarding participation in this study, the subject can contact the following investigators:

for Brescia Site: [name] (Principal Investigator) – [contact].

Adverse Events (AEs) and Serious Adverse Events (SAEs) are defined by the ICH Guideline Medical Device Directive 93/43/EEC and Guidelines on Medical Devices MEDDEVG 2.7/3rev. 3,

May 2015 Clinical Investigations: Serious Adverse Event Reporting under Directives 90/385/EEC and 93/42/EEC for Good Clinical Practice (ICH GCP) as follows:

An adverse event (AE) is any untoward medical occurrence, unintended disease or injury or any untoward clinical signs (including an abnormal laboratory finding) in subjects, users or other persons whether or not related to the investigational medical device.

With respect to intensity, adverse events are classified as follows:

- Mild Some awareness of symptoms, but easily tolerated;
- Moderate Symptoms causing enough discomfort to interfere with usual activity;
- Severe Incapacitating event causing inability to work or to perform usual activity.

Adverse events are classified as either non-serious or serious.

Serious Adverse Event (SAE) is an adverse event that:

- a) led to a death;
- b) led to a serious deterioration in health of the subject, that either resulted in:
 - a life-threatening illness or injury, or
 - a permanent impairment of a body structure or a body function, or
 - in-patient hospitalization or prolongation of existing hospitalization, or
 - in medical or surgical intervention to prevent life threatening illness or
 - injury or permanent impairment to a body structure or a body function.
- c) led to fetal distress, fetal death or a congenital abnormality or birth defect.

Device deficiency: inadequacy of an investigational medical device related to its identity, quality, durability, reliability, safety or performance. This may include malfunctions, use error, or inadequacy in the information supplied by the manufacturer.

AEs include any clinically significant deterioration of a subject's medical status, after being enrolled and signing an informed consent form. The AE may involve any organs or systems and can be represented by the new onset or the deterioration of a disease, a syndrome, a symptom, a physical sign, as well as by findings and results of instrumental examinations and laboratory tests. Any medically relevant and untoward change from baseline, including frequency or pattern changes for a fluctuating condition (e.g., migraine), occurring after the administration of investigated treatments

is an adverse event. All such occurrences must be recorded and reported accordingly, whether they appear causally related to the study medication, or not.

Serious Adverse Device Effect (SADE) is an adverse device effect that has resulted in any of the consequences characteristic of a serious adverse event.

Unanticipated Serious Adverse Device Effect (USADE) is a serious adverse device effect which by its nature, incidence, severity or outcome has not been identified in the current version of the risk analysis report or investigator's brochure (IB).

NOTE: Anticipated SADE (ASADE): an effect which by its nature, incidence, severity or outcome has been previously identified in the risk analysis report or IB.

The following events are considered reportable:

- any SAE;
- any Device Deficiency that might have led to a SAE if:
 - a) suitable action had not been taken or
 - b) intervention had not been made or
 - c) if circumstances had been less fortunate;
- new findings/updates in relation to already reported events.

Reportable events have to be reported by clinical investigators.

Assessment of Causality

The following criteria are to be used for the assessment of the causal relationship to the test/control treatment. For classification, all criteria of one of the following categories must be met:

related, if

- a timely correlation exists and
- dechallenge and/or rechallenge and
- a biological plausibility exists and
- other factors are clearly excluded
- a medical report or clinical proof exists;

possibly related, if

- a timely correlation exists and
- dechallenge and/or rechallenge and
- a biological plausibility exists and
- a medical report or clinical proof does not exist;

unrelated, if

- a timely correlation does not exist or is uncertain and
- dechallenge and/or rechallenge does not exist and
- a biological plausibility exists and
- a medical report or a clinical proof does not exist;

unknown, if

- not enough information exists for evaluation
- no further contact with reporter possible.

Sound medical/clinical judgment will be applied when assessing the causality and seriousness of the adverse events.

Adverse Event Reporting

The study center will provide the study participants with emergency telephone numbers for study related support and feedback. The emergency telephone number is operated by either an investigator of the study or by a qualified person designated by the principal investigator. The schedule of reachability of the emergency telephone number will be defined prior to start of the study.

Serious Adverse Events

The Investigator shall immediately after awareness (and in any event, not later than within 24 hours after awareness) inform the PI. The Investigator will send the SAE report to the following email address: [contact]. Appendix 3 has to be used for SAE reporting. Form has to be completed electronically and in English.

Adverse Events

Adverse events will be assessed by the investigator or designee within 24 hours for severity, relationship to the study product, possible etiologies, and whether the event meets the criteria as a

serious adverse event and therefore requires immediate notification to the PI. For data collection purposes, the outcome of all adverse events recorded on the Adverse Reaction section of the CRF will be designated as of the completion of the final evaluation or examination. However, the investigator is responsible for following all adverse events until resolution or until no longer of clinical concern, and providing these data to the PI. At the end of the study, the investigator will report all adverse events (serious and non-serious) to the PI on CRFs. Forms have to be completed electronically and in English.

Pregnancy

No pregnant women (according to medical history) will intentionally be enrolled in this study. In the event a woman enrolled in this clinical research study becomes pregnant during the course of the study, participation in this study will be terminated upon the clinical staff's notification of the event. The subject's medical records used in this study will be updated to reflect the pregnancy and there will be follow-up contact until the end of the pregnancy to record the outcome in the clinical file.

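### The *unrelated* causality category wrongly requires biological plausibility and, read literally, the categories leave some well-documented adverse events unclassified

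*Combined protocol and SAP*

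**What the plan says.** Section 8, Assessment of Causality, gives four categories (*related*, *possibly related*, *unrelated*, *unknown*) under one rule: "For classification, all criteria of one of the following categories must be met".

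- *Related* needs a fitting time course, the dechallenge/rechallenge line, plausibility, "other factors are clearly excluded", and a report or proof.
- *Possibly related* needs the first three of these and that "a medical report or clinical proof does not exist". It is silent on other factors.
- *Unrelated* has four lines. The first is "a timely correlation does not exist or is uncertain and", the second is "dechallenge and/or rechallenge does not exist and", the third asks that plausibility be present, in the same words as the two categories above, and the last is "a medical report or a clinical proof does not exist".
- *Unknown* has two lines with no connecting word: "not enough information exists for evaluation", and that the reporter can no longer be contacted.

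The list closes with: "Sound medical/clinical judgment will be applied when assessing the causality and seriousness of the adverse events". The later text on adverse events asks for relationship to the product to be assessed within 24 hours.

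Section 4, Evaluation of Safety, plans a per-group count of AEs rated possibly related or higher. It does not say how *unknown* or unclassified AEs are shown.

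**The concern.** A conjunctive rule works only if the criteria are right and the categories together cover every case. The plausibility line under *unrelated* looks like a carry-over from the categories above it. Its effect is that the AE an investigator would most readily call unrelated, one with no conceivable link to the lozenge, cannot be given that label.

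The same rule also raises the question of where timely, plausible AEs go when they miss a single line of *possibly related*. If they get no label, they drop out of the Section 4 count although nothing in the protocol says that is intended. Two assessors could also treat the same AE differently and both claim to follow the text.

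**Working it through.** The plan gives no figure to reproduce, and the check is one of logic. It covers AEs with enough information to assess, so *unknown* is set aside.

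**Step 1. The criteria side by side (Section 8).**

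| Fact about the AE | Related | Possibly related | Unrelated |
|---|---|---|---|
| Timing fits | yes | yes | no or uncertain |
| Dechallenge/rechallenge | listed, no verb | listed, no verb | absent |
| Plausible | yes | yes | yes |
| Other factors excluded | yes | not mentioned | not mentioned |
| Report or proof | present | absent | absent |

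**Step 2. The plausibility line.** The third row is *yes* throughout. An implausible AE fails all three categories, and with adequate information it is not *unknown*. Correcting the line under *unrelated* leaves the two upper categories untouched, so the Section 4 count does not move on this ground.

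**Step 3. Two further gaps on a literal reading.**

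- *Gap 1.* The dechallenge/rechallenge line has no verb in the two upper categories. If it means that one must be present, a timely, plausible AE without either is neither *related* nor *possibly related*. It is not *unrelated* either, because its timing fits. Lozenges are taken for 3 weeks (Section 1, Visit 2), so an AE still present then has a built-in dechallenge. An AE that settles while dosing continues has none.
- *Gap 2.* A timely, plausible AE with dechallenge and a medical report, but with other factors not excluded, fails *related* on other factors and *possibly related* because a report exists. It is better documented than *possibly related* asks, yet falls outside it.

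**Step 4. Enumeration.** Take timing at three levels (yes, no, uncertain) and the other four facts as yes/no: 3 × 2 × 2 × 2 × 2 = 48 patterns. Literally, *related* takes 1, *possibly related* 1 × 2 = 2 (other factors free), and *unrelated* 2 × 2 = 4 (two timing levels, other factors free). That is 1 + 2 + 4 = 7 classified and 48 − 7 = 41 not. No pattern falls in two categories.

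The two ambiguous lines give four readings:

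| Reading | Classified (related + possibly + unrelated) | No category, of 48 | Implausible, no category, of 24 | Timely and plausible, no category, of 8 |
|---|---|---|---|---|
| A: literal | 1 + 2 + 4 = 7 | 41 | 24 | 5 |
| B: a report counts only as proof of cause (other factors excluded) | 1 + 3 + 6 = 10 | 38 | 24 | 4 |
| C: dechallenge/rechallenge not required in the two upper categories | 2 + 4 + 4 = 10 | 38 | 24 | 2 |
| D: both B and C | 2 + 6 + 6 = 14 | 34 | 24 | 0 |

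Under A the 5 are the four patterns without dechallenge/rechallenge (gap 1) plus one for gap 2. The plausibility defect holds on all four readings. Gaps 1 and 2 shrink and then vanish as the lines are read more generously. These are counts of logical patterns, not of events; the documents give no AE rates.

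**Step 5. Does correcting the plausibility line suffice?** On reading A, reversing it still leaves *unrelated* with 4 patterns and 41 without a category. Deleting it gives *unrelated* 8, so 1 + 2 + 8 = 11 are classified and 48 − 11 = 37 are not. The other lines need attention too.

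**The case against.** **The count is still determinate.** Once the dechallenge/rechallenge line is read one way, counting the AEs that meet *related* or *possibly related* gives a definite number, and the two do not overlap. This stands. A reader might infer that the Section 4 count is undefined, but the documents do not support that. The supportable statement is that the count may leave out AEs whose exclusion the protocol does not say it intends.

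**Uncertain timing.** A reader might infer that letting uncertain timing lead to *unrelated* is also an error. It is a stated rule, applied with three further criteria. One may dislike it, but it is neither a contradiction nor a gap. Nor does the text say whether uncertain timing could count as too little information.

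***Unknown* could absorb some cases.** Its two lines have no connecting word. If lack of information is enough alone, some AEs would go there. This is why the check is limited to AEs with adequate information.

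**Judgment and data review soften the effect.** Section 8 invokes clinical judgment. Section 7 provides for checks of the CRFs by the principal investigator, documented queries and a blind data review meeting before lock. These are real routes for resolving unclassified AEs, but none names a default category, and the judgment sentence stands beside a rule that every criterion be met.

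**Dechallenge can occur during treatment.** Section 4 foresees AEs that lead to stopping or reducing treatment. That narrows gap 1 without closing it.

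**Forms not seen.** The CRF and the SAE form are not in the supplied text and may carry their own causality field.

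**Conclusion.** The plausibility line under *unrelated* is wrong as written, and read literally the categories are not exhaustive for AEs with enough information. Confidence in both statements is high. That the Section 4 count may be too low is held with moderate confidence, because gaps 1 and 2 depend on how the dechallenge/rechallenge and report-or-proof lines are read; on the most generous reading tested they disappear. The size of any undercount cannot be estimated from the documents.

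Two further inferences are tempting and unsupported. The pattern counts are not shares of events. Nor does collecting AEs to 6 months (Study Flow Chart) against 3 weeks of lozenges show a loss of related AEs, since a late AE may simply lack a fitting time course. No difference between groups is claimed, given the blinding.

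Total AEs, patients with at least one AE and efficacy are unaffected. So is SAE reporting, which does not depend on causality (Section 2, Implementation; Section 8). Severity is minor.

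**What to change.** 1. In Section 8, correct the plausibility line under *unrelated* so that it no longer requires plausibility.
2. Reconcile Sections 4 and 8 so that every AE has exactly one category. The text should make clear whether dechallenge/rechallenge must be present, where a documented AE with other factors not excluded belongs, and whether both *unknown* lines must be met. The criteria themselves are for the sponsor and investigators to set.
3. In the Section 4 safety table, show *unknown* or unclassified AEs as a separate row per group.

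The cost is small wording changes, one extra table row, and a check that the CRF and SAE form match the revised categories.

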 - changes in the following clinical parameters: Pocket closure, REC (Clinical Gingival Recession), CAL (Clinical Attachment Level), BOP (Bleeding on Probing), PI (Plaque Index).
 - Risk progression of the periodontitis and the need of periodontal surgery.
- c. Microbiological outcomes: changes in microbial composition and proportion of sequences identified as *Lactobacillus reuteri* in the deepest residual pockets.

STUDY POPULATION

Forty-four (44) adults, aged 18-75 years, will be entered into study (randomized). It is expected that forty (40) subjects will complete the study.

Randomized subjects who deviate from the protocol (major protocol deviation) and, for this reason, are excluded from the analysis, will be replaced to guarantee that the sample required for the analysis (40) is reached.

Patients will be treated at the Department of Surgical Specialities Radiological Science and Public Health, School of Dentistry, Section of Periodontics, Brescia, Italy from 04/2020.

Inclusion Characteristics

- Signed Informed Consent Form.
- Male and female subjects, aged 18-75 years, inclusive.
- Good general health (free of systemic diseases such as diabetes, HIV infection or genetic disorder, ongoing malignant disease of any type that could influence the outcome of the treatment and might interfere with the evaluation of the study objectives).
- History of periodontitis staging III or IV grading B or C
- At least 2 sites with probing depth ≥ 6 mm or pockets of 5 mm with bleeding on probing in two different quadrants.
- Previous periodontal non-surgical treatment at least 3 months maximum 6 months.
- Availability for the 6-month duration of the study for an assigned subject.

Exclusion Characteristics

- Not willing to follow the agreed protocol.
- Presence of orthodontic appliances.
- Smokers more than 10 cigarettes per day
- Chronic obstructive pulmonary disease and asthma.
- Tumors or significant pathology of the soft or hard tissues of the oral cavity.
- Current radiotherapy or chemotherapy.
- Pregnant or lactating women.
- Current or past (within 3 months prior to enrollment) assumption of medications that may influence periodontal conditions and/or interfere with healing following periodontal treatment (i.e., corticosteroids, calcium channel blockers, systemic antibiotics, ...).
- History of allergy to Erythritol or chlorexidine.

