1. STUDY DESIGN

The study design was chosen according to the current standards required by ISO, GCP and according to national requirements.

- a. A Parallel-Arm, Statistician, Operator and Examiner are blinded, RCT will be established;
- b. The RCT will be run as mono-center;
- c. A total of 44 subjects will be recruited to participate in the study. It is expected that all of 40 subjects will complete the study in total;
- d. Admission into the study will be via rolling admission (estimated recruitment time: 12 months);
- e. Each subject must have at least 2 residual sites/pockets with probing depth ≥ 6 mm or pockets of 5 mm with bleeding on probing in two different quadrants;
- f. Each subject will follow the following treatment protocol:
 - i. – Visit 1 (Screening): (within 29 days prior to baseline) – consent secured; screening and entry into study; baseline data collection; full periodontal charting (full-mouth PD, REC, BOP, PI); identification the sites for microbiological sample.
 - ii. – Visit 2 (T0 – Baseline Visit+Treatment): collection of microbiological samples from the two deepest sites in two different quadrants. All patients receive a full mouth periodontal treatment (GBT) and OHI (oral hygiene instruction). According to the list of randomization the patient will be allocated into one of the two arm of probiotic treatment: study lozenges are given to all patients to consume at home. The patients are instructed to dissolve these on their tongue twice a day, preferably after brushing, for 3 weeks. The patients of the probiotic group will receive probiotic lozenges containing *Lactobacillus reuteri* DSM 17938 and *Lactobacillus reuteri* ATCC PTA 5289 (a minimum of 2×10^8 colony-forming units L. reuteri Prodentis/lozenge, BioGaia AB). The patients of the control group will receive control lozenges without live bacteria. Furthermore, the probiotic and control lozenges will be identical in taste, texture and appearance.
 - iii. – Visit 3 (T1) – 3 weeks: the participants will be asked to return the empty packages of the study medication to examine the adherence. At that time, side effects will also be questioned by the examiner by means of an open question. Collection of the

microbiological sample will be performed from the same subgingival sites as during Baseline (T0) and reinforcement of OHI.

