iv. – Visit 4 (T2) - 3 months: Collection of the microbiological sample from the same subgingival sites as during Baseline (T0), collection of full periodontal charting (PD, REC, PI, BOP) and reinforcement of OHI.

v. – Visit 5 (T3) - 6 months: Collection of the microbiological sample from the same subgingival sites as during Baseline (T0), collection of full periodontal charting (PD, REC, PI, BOP) and full mouth GBT will be done in both groups. Subjects will either be entered into a routine recall system for treatment or scheduled for any further periodontal treatment as clinically indicated, and exit the study.

- g. All treatments are made by the same clinician;
- h. Calibration: the examiner is calibrated showing an intra-examiner reproducibility of 96% for duplicate measurement of probing pocket depth (PPD) with a maximum difference of 1 mm in 5 patients;
- i. Data collection: A PCP-UNC 15 periodontal probe is used on six sites per tooth (mesio-buccal, buccal, disto-buccal, mesio-lingual, lingual and disto-lingual) with a gentle probing force by the same clinician. Measurements are rounded to the nearest millimeter;
- j. Clinical assessment data will be recorded via hard copy CRFs. CRFs will be submitted to a data entry staff member for entry into the statistical database. At the conclusion of the study, such statistical database will be submitted to the statistician for the preparation of the statistical analysis and the final study report.

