zOTUs that taxonomically will be assigned to genus *Lactobacillus*, will be analyzed separately, in order to assess if the probiotic strains have established in the oral cavity. For this, first, a phylogenetic tree will be created based on the representative sequence of each zOTU. Sequences that will be phylogenetically related to *L. reuteri* 16S rRNA gene fragment amplified, will be marked as potential probiotic sequences. Relative abundances of all genus lactobacillus sequences and *L. reuteri* sequences between groups per timepoint will be compared.

Concomitant Therapy

A necessary concomitant medication or therapy is permitted as long as it is not excluded in the exclusion criteria. Every medication has to be reported in the CRF (Appendix 1) and in the

Concomitant Medication form (Appendix 2). All changes during the study are to be reported in the CRF. Usage of prohibited therapy will lead to the exclusion of the subject.

Blinding and Randomization

Blinding: The statistician will be blinded to the group identification. The patient and the operator will not know the treatment. Knowledge of the randomization list will be limited to the persons responsible for creation of the randomization list, provider of randomization numbers to study site, and delivery of the test/control treatment until the last subject (i.e. final examination of the last subject), quality control and verification of the CRFs is completed.

Randomization and allocation concealment: The randomization of the study protocols will be performed by a staff member who is not further involved in this study. This will be done based on a computer-generated table (www.randomization.com) that links each patient to one of the treatment groups. The same staff member will be responsible for blinding the study products. This will be done by labelling the packaging of these products with a letter indicating the treatment group. Additionally, the jars containing the lozenges will be identical in appearance and non-transparent. When a patient will be included in the study, the study medication will be handed out to the researcher according to group to which that patient will be assigned based on the patient number and the randomization list. The similarity of the packaging, and the identical appearance, texture and taste of the study products make the double-blinding of the researcher and patient possible.

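### Prohibited therapy after randomisation leads to an undefined exclusion, and no rule keeps that patient's 3- and 6-month PD in the primary analysis

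*Combined protocol and SAP*

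**What the plan says.** - **Prohibited therapy.** Section 2, Concomitant Therapy: "A necessary concomitant medication or therapy is permitted as long as it is not excluded in the exclusion criteria". Then: "Usage of prohibited therapy will lead to the exclusion of the subject". The object of the exclusion (lozenges, visits or analysis) is not given. The exclusion criteria that define prohibited therapy cover "medications that may influence periodontal conditions and/or interfere with healing following periodontal treatment", with corticosteroids, calcium channel blockers and systemic antibiotics as examples.
- **Deviators.** Study Population: "Randomized subjects who deviate from the protocol (major protocol deviation) and, for this reason, are excluded from the analysis, will be replaced", so that 40 patients are analysed. No text says whether prohibited therapy is a major deviation.
- **Pregnancy.** Section 8: "participation in this study will be terminated upon the clinical staff's notification of the event". The only later contact described is for the outcome of the pregnancy.
- **Other withdrawals.** Section 6 is permissive: "Subjects could be withdrawn from the study if any of the following occur". A serious adverse reaction is on that list, so the investigator may already keep such a patient in the study.
- **Timing.** In section 1, patients "dissolve these on their tongue twice a day, preferably after brushing, for 3 weeks". After baseline, PD is charted only at 3 and 6 months. The 6-month entry reads "collection of full periodontal charting (PD, REC, PI, BOP) and full mouth GBT will be done in both groups".
- **Analysis.** Section 4 names a mixed model for PD with a random patient effect. It gives no efficacy analysis set and no rule for missing PD. The safety set is the only one defined.

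**The concern.** The protocol does not separate stopping the lozenges from leaving the study or the analysis. After day 21 there is no product left to stop, so removing a patient then avoids no exposure and costs primary-outcome data.

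Prescriptions made after randomisation are not a neutral reason for loss. The protocol itself treats these medicines as able to affect the periodontium. If an antibiotic is given for a pocket that is getting worse (an assumption; the documents report no such cases), the rule removes a patient who is doing badly. If this happens more in one arm, the estimated PD difference is biased. Replacing the patient restores the count of 40 but not the randomised patient's result.

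Pregnancy raises the same issue more weakly. Charting still due is lost, but nothing in the documents links pregnancy to arm or to PD.

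**Working it through.** **1. The plan's own figure.** Inputs from section 4: difference 1 mm, patient SD 0.974, residual SD 1.65, 7 sites per patient, 20 per group, alpha 0.05 (taken as two-sided; the side is not stated).

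- SD of a patient mean = √(0.974² + 1.65²/7) = √(0.949 + 0.389) = 1.157 mm.
- n per group for 80% power = 2 × 7.849 × 1.157² / 1² = 21, against 20 stated.
- Power at 20 per group = Φ(1/(1.157 × √(2/20)) − 1.96) = Φ(0.774) = 78.1%, against at least 80% stated.
- 20 × 1.10 = 22 per group, 44 in total.

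The simple formula comes within one patient per group and two points of power of the planned simulation. The sample size is not in question here, and keeping patients does not change it.

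**2. What each reading of exclusion costs.** Planned post-baseline readings are 7 sites × 2 visits = 14 per patient, and 44 × 14 = 616 in all.

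| Excluded from | Event before the 3-month visit | Event between 3 and 6 months |
|---|---|---|
| Lozenges only | 0 | 0 |
| Study (later visits) | 14 (14/616 = 2.3%) | 7 (7/616 = 1.1%) |
| Analysis | 14 (2.3%) | 14 (2.3%) |

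The first reading loses no PD, but after day 21 it has no content. The second row assumes that a 3-month value already charted is used: no rule discards it, though the plan does not commit to using it. Pregnancy follows the second row.

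**3. Illustrative bias.** Assumptions: k of 22 patients are removed in one arm only, and their mean PD change differs by d from the rest of that arm. The arm mean then shifts by k × d / 22.

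- k = 1, d = 0.5 mm: 0.023 mm
- k = 1, d = 1 mm: 0.045 mm
- k = 2, d = 0.5 mm: 0.045 mm
- k = 2, d = 1 mm: 0.091 mm

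With two removed in one arm and one in the other, both at d = 1 mm, the net shift is 2/22 − 1/22 = 0.045 mm. Equal numbers with equal d give 0.

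**4. The cost of keeping a patient.** If another medicine moves a retained patient's PD by 1 mm, the arm mean moves by 1/22 = 0.045 mm. Retention therefore has its own price, and both results should be shown.

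**The case against.** The strongest reply is that setting aside values taken after a confounding medicine is a legitimate aim, and that step 4 shows a retained patient can move the arm mean as much as a removed one. This stands as a reason to report both analyses. It does not justify removing and replacing randomised patients in the primary one: that conditions on an event after randomisation which may reflect outcome, and the retained values can still be set aside in a sensitivity analysis.

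The blinding and the blind data review before database lock (section 7) make exclusion decisions that depend on arm less likely. That also stands. The review neither recovers charting that was never done nor sets an analysis set.

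For pregnancy, ending research participation is a cautious ethical choice, and pregnancy is not evidently a protocol deviation, so the replacement rule need not apply.

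A reader might infer three stronger conclusions, which the documents do not support:

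- **A raised false-positive rate.** If the lozenge affects neither PD nor removal, removal under blinding is exchangeable between arms, even when it depends on outcome. A chance split of two against none is sampling variation. Inflation would need a lozenge that changes removal without changing PD, and nothing in the documents points to that.
- **A loss of power against the plan.** The plan is powered on 20 per group. By the method in step 1, 20 and 22 patients give 79.9%, above the 78.1% for 20 and 20. Two removals also fit within the four-patient dropout allowance.
- **That PD is lost on every reading.** Exclusion from lozenges only loses none, and no rule discards a 3-month value charted before a pregnancy.

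**Conclusion.** The point holds in limited form. Exclusion for prohibited therapy is mandatory but undefined, and on two of its three readings it takes a randomised patient's PD out of the primary comparison for a reason that may relate to outcome. Pregnancy is a secondary instance: only charting still due is lost.

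The documents give no rate for either event, so the number affected may be zero. The 0.02 to 0.09 mm range is an illustration that rests on one-sided removal of 1 or 2 patients with d of 0.5 to 1 mm. There is no bias if removal is equal in both arms and unrelated to outcome. This is a cheap improvement: the case rests on how little the change costs, not on a large expected error.

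**What to change.** - **Section 2, Concomitant Therapy:** state that prohibited therapy ends the lozenges if they are still being taken, and does not end follow-up. Keep consenting patients in the planned 3- and 6-month PD charting.
- **Study Population:** state that prohibited therapy after randomisation is not a reason for exclusion from the primary analysis or for replacement.
- **Section 4:** analyse all available PD by randomised arm. Flag values taken after a prohibited medicine and repeat the primary model without them as a sensitivity analysis.
- **Section 8, Pregnancy:** allow PD charting to continue if the patient consents and the investigator judges it safe, with GBT and plaque sampling at the investigator's discretion.
- **Section 6:** a clarifying sentence that withdrawal from lozenges need not mean withdrawal from charting is enough. Withdrawal of consent remains a reason to leave, as section 11 already provides.

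**Cost.** This needs an amendment with prior approval (section 9), possibly with updated consent text for pregnant patients. Because Study Population rules out design changes after ethics approval, it is best made before that approval. No visits or data items are added: both charting visits are planned, and the flow chart already records concomitant therapy at every visit. The downside is that some retained values will reflect other medicines, which is why the flag and the sensitivity analysis are needed.
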